#### **5.4. Screen Failures**

Screen failures are defined as participants who consent to participate in the clinical study but are not subsequently randomly assigned to study intervention/enrolled in the study. Screen failure data are collected and remain as source and are not reported to the clinical database.

Individuals who do not meet the criteria for participation in this study (screen failure) may not be rescreened.

### **6. STUDY INTERVENTION**

Study intervention is defined as any investigational intervention(s), marketed product(s), placebo, medical device(s), or study procedure(s) intended to be administered to a study participant according to the study protocol.

For the purposes of this protocol, study intervention refers to PF-07038124 0.01% ointment and PF-07038124 vehicle ointment.

## 6.1. Study Intervention(s) Administered

Intervention Name	PF-07038124 0.01% ointment	PF-07038124 vehicle ointment
ARM Name (group of patients receiving a specific treatment (or no treatment)	Active	Vehicle
Type	Drug	Drug
Dose Formulation	Ointment	Ointment
Unit Dose Strength(s)	0.1 mg/g ointment in 60-gram tube	0 mg/g ointment in 60-gram tube
Dosage Level(s)	0.01% (wt/wt), QD	0% (wt/wt), QD
Route of Administration	Topical	Topical
Use	Experimental	Placebo
IMP or NIMP	IMP	IMP
Sourcing	Provided centrally by the sponsor.	Provided centrally by the sponsor.
Packaging and Labeling	Study intervention will be provided in cartons. Each carton will contain one tube. Both the carton and tube will be labeled in a blinded format as required per country requirement.	Study intervention will be provided in cartons. Each carton will contain one tube. Both the carton and tube will be labeled in a blinded format as required per country requirement.

PF-07038124 topical ointment, 0.1 mg/g will be provided as the active ingredient with precedented excipients: white petrolatum, mono- and di-glycerides, hexylene glycol and paraffin wax.

Vehicle (placebo, no active drug in the formulation) topical ointment will be provided as the precedented excipients only: white petrolatum, mono- and di-glycerides, hexylene glycol and paraffin wax.

PF-07038124 and vehicle ointments will be supplied by Pfizer to the CRU as 60 gram tubes and labeled according to local regulatory requirements in a blinded fashion.

During the stay in the CRU, study intervention applications will be performed by trained study staff to ensure proper study intervention application.

### 6.1.1. Administration

#### 6.1.1.1. Study Treatment Regimen

The study intervention will be applied in blinded fashion, at the CRU. All applications of the study intervention will be dispensed and applied by study site staff from Day 1 through Day 10 dose. Every effort must be made for the dose applications on Days 2-10 to be completed at  $24 \pm 2$  hour intervals from the recorded time of completion of the Day 1 dose application, for each participant.

The study intervention will be applied QD for 10 consecutive days from Day 1 AM through Day 10 AM.

The per application dose will be calculated using the formula provided below in [Section 6.1.1.2](#). The intended dose of the study intervention application is approximately

3 mg/cm^2. The study intervention should be applied evenly to all identified areas. The per application dose will be expressed as the weight of ointment in grams. The per application dose will remain fixed and the study intervention will be applied to the areas identified on Day 1.

#### **6.1.1.2. Calculation of Per Application Dose**

The per application dose (expressed in g) will be calculated by study site staff, for each participant, using the formula below:

$$\text{BSA} \times 0.003 \text{ (g/cm}^2\text{)} = \text{Weight of study intervention (in g) per application.}$$

where BSA is 2000 cm^2 for Cohort 1, and 4000 cm^2 for Cohort 2.

#### **6.1.1.3. Application of Study Intervention**

Before the Day 1 AM dose is applied for each participant, the designated areas for treatment will be identified on Day 1 and documented in the participant's study records. For each subsequent study intervention application, study site staff will refer to the documented locations as determined on Day 1.

The application area will include a treatment area of 2000 cm^2±200 cm^2 (approximately 10% BSA) for Cohort 1. For Cohort 2, the treatment area is 4000 cm^2±400 cm^2 (approximately 20% BSA). The study intervention will be applied for 10 consecutive days. The application area will include the back as well as other extremities, abdomen and/or chest, identified by the investigator.

Wearing gloves, study site staff will apply the per application dose to the surface area determined on Day 1. Study intervention will be applied as a thin layer of participant's skin. Care must be taken to avoid study intervention contamination of designated venous access areas used for PK sampling, by leaving an untreated margin of at least 5 cm radius around each venipuncture site. Following study intervention application, participants will be instructed to wear loose-fitting clothing, to not wipe study intervention off the skin, and to refrain from bathing, sauna or washing the treated areas within 4 hours after application. At 4 hours post-dose, study intervention will be wiped from all application sites, with a clean towel, prior to participants being released to shower.

### **6.2. Preparation/Handling/Storage/Accountability**

1. The investigator or designee must confirm appropriate temperature conditions have been maintained during transit for all study interventions received and any discrepancies are reported and resolved before use of the study intervention.
2. Only participants enrolled in the study may receive study intervention and only authorized site staff may supply or administer study intervention. All study interventions must be stored in a secure, environmentally controlled, and monitored (manual or automated recording) area in accordance with the labeled storage conditions with access limited to the investigator and authorized site staff. At a

minimum, daily minimum and maximum temperatures for all site storage locations must be documented and available upon request. Data for nonworking days must indicate the minimum and maximum temperatures since previously documented for all site storage locations upon return to business.

3. Any excursions from the study intervention label storage conditions should be reported to Pfizer upon discovery along with any actions taken. The site should actively pursue options for returning the study intervention to the storage conditions described in the labeling, as soon as possible. Once an excursion is identified, the study intervention must be quarantined and not used until Pfizer provides permission to use the study intervention. Specific details regarding the definition of an excursion and information the site should report for each excursion will be provided to the site in the IP manual.
4. Any storage conditions stated in the SRSD will be superseded by the storage conditions stated on the label.
5. Study interventions should be stored in their original containers.
6. The head of the medical institution (where applicable) or study intervention administrator is responsible for study intervention accountability, reconciliation, and record maintenance (ie, receipt, reconciliation, and final disposition records), such as the IPAL or sponsor-approved equivalent. All study interventions will be accounted for using a study intervention accountability form/record.
7. Further guidance and information for the final disposition of unused study interventions are provided in the IP manual. All destruction must be adequately documented. If destruction is authorized to take place at the investigator site, the investigator must ensure that the materials are destroyed in compliance with applicable environmental regulations, institutional policy, and any special instructions provided by Pfizer.

Upon identification of a product complaint, notify the sponsor within 1 business day of discovery as described in the IP Manual.

### **6.2.1. Preparation and Dispensing**

Within this protocol, preparation refers to the investigator site activities performed to make the study intervention ready for administration or dispensing to the participant by qualified staff. Dispensing is defined as the provision of study intervention, concomitant treatments, and accompanying information by qualified staff member(s) to a healthcare provider, participant in accordance with this protocol. Local health authority regulations or investigator site guidelines may use alternative terms for these activities.

The study intervention will be dispensed in a blinded fashion using an IRT system at the study days as summarized in the [SoA](#). A qualified staff member will dispense the study

intervention via unique container numbers on the cartons provided. A second staff member will verify the dispensing.

Prior to application, the per application dose will be carefully weighed out by the qualified CRU staff. Blinded study intervention will be applied to the participant.

### **6.3. Measures to Minimize Bias: Randomization and Blinding**

#### **6.3.1. Allocation to Study Intervention**

Allocation of participants to treatment groups will proceed through the use of an IRT system (IWR). The site personnel (study coordinator or specified designee) will be required to enter or select information including but not limited to the user's ID and password, the protocol number, and the participant number. The site personnel will then be provided with a treatment assignment, randomization number, and DU or container number when study intervention is being supplied via the IRT system. The IRT system will provide a confirmation report containing the participant number, randomization number, and DU or container number assigned. The confirmation report must be stored in the site's files. Study intervention will be dispensed at the study days as summarized in the [SoA](#).

The study-specific IRT reference manual and IP manual will provide the contact information and further details on the use of the IRT system.

#### **6.3.2. Breaking the Blind**

The IRT will be programmed with blind-breaking instructions. In case of an emergency, the investigator has the sole responsibility for determining if unblinding of a participant's treatment assignment is warranted. Participant safety must always be the first consideration in making such a determination. If the investigator decides that unblinding is warranted, the investigator should make every effort to contact the sponsor prior to unblinding a participant's treatment assignment unless this could delay further management of the participant. If a participant's treatment assignment is unblinded, the sponsor must be notified within 24 hours after breaking the blind. The date and reason that the blind was broken must be recorded in the source documentation and CRF.

The study-specific IRT reference manual and IP manual will provide the contact information and further details on the use of the IRT system.

### **6.4. Study Intervention Compliance**

The study intervention will be applied by the investigator site personnel. The application site of each participant will be examined following dosing by the second staff member to ensure the study intervention was topically applied. The date and time of each dose administered in the clinic will be recorded in the source documents and recorded in the CRF. The dose of study intervention and study participant identification will be confirmed at the time of dosing by a member of the study site staff other than the person administering the study intervention.

## **6.5. Concomitant Therapy**

Use of prescription or nonprescription drugs and dietary and herbal supplements are prohibited within 14 days or 5 half-lives (whichever is longer) prior to the first dose of study intervention. Limited use of nonprescription medications that are not believed to affect participant safety or the overall results of the study may be permitted on a case-by-case basis following approval by the sponsor. Acetaminophen/paracetamol may be used at doses of  $\leq 1$  g/day.

Hormonal contraceptives that meet the requirements of this study are allowed to be used in participants who are WOCBP (see [Appendix 4](#)).

All concomitant treatments taken during the study must be recorded with indication, daily dose, and start and stop dates of administration. All participants will be questioned about concomitant treatment at each clinic visit.

Treatments taken within 28 days before the first dose of study intervention will be documented as a prior treatment. Treatments taken after the first dose of study intervention will be documented as concomitant treatments.

### **6.5.1. Rescue Medicine**

There is no rescue therapy to reverse the AEs observed with PF-07038124; standard medical supportive care must be provided to manage the AEs.

## **6.6. Dose Modification**

Not applicable.

## **6.7. Intervention After the End of the Study**

No intervention will be provided to study participants at the end of the study.

## **7. DISCONTINUATION OF STUDY INTERVENTION AND PARTICIPANT DISCONTINUATION/WITHDRAWAL**

### **7.1. Discontinuation of Study Intervention**

In rare instances, it may be necessary for a participant to permanently discontinue study intervention (definitive discontinuation). Reasons for definitive discontinuation of study intervention include the following: Liver injury, ECG changes, local tolerability, and AEs.

Note that discontinuation of study intervention does not represent withdrawal from the study. If study intervention is definitively discontinued, the participant will remain in the study to be evaluated for follow up. See the [SoA](#) for data to be collected at the time of discontinuation of study intervention and follow-up for any further evaluations that need to be completed.

In the event of discontinuation of study intervention, it must be documented on the appropriate CRF/in the medical records whether the participant is discontinuing further receipt of study intervention or also from study procedures, posttreatment study follow-up, and/or future collection of additional information.

The site will inform the Sponsor Medical Monitor or Sponsor Clinician if the below criteria for permanent discontinuation of the study intervention are triggered.

### **Liver Injury**

Please refer to [Appendix 6](#) for Potential Cases of Drug-Induced Liver Injury (DILI; Hy's law).

### **ECG Changes**

A participant who meets either bulleted criterion based on the average of triplicate ECG readings will be withdrawn from the study intervention.

- QTcF >500 msec.
- Change from baseline: QTc >60 msec.

If a clinically significant finding is identified (including, but not limited to, changes from baseline in QTcF after enrollment), the investigator or qualified designee will determine if the participant can continue in the study and if any change in participant management is needed. This review of the ECG printed at the time of collection must be documented. Any new clinically relevant finding should be reported as an AE.

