#### Schedule of Activities

Visit Identifier a Abbreviations used in this table may be found in Appendix 8 .	Screening		Treatment Phase											Follow-Up b	Early Termination/ Discontinuation
Days Relative to Day 1	-28 to -2	-1	1	2	3	4	5	6	7	8	9	10	11	38+3	
Informed consent	X														
CRU confinement c		X	→	→	→	→	→	→	→	→	→	→	→		
Outpatient visit	X														
Inclusion/exclusion criteria	X	X	X												
Randomization			X												
Medical/medication history (update)	X	X													
Physical exam d	X	X													X
Height and weight	X														
Review prior or concomitant treatments, as applicable	X	→	→	→	→	→	→	→	→	→	→	→	→	X	X
Safety laboratory, including fibrinogen and hsCRP e	X	X				X						X	X		X
Demography	X														
Contraception check	X	X												X	X
Single, supine 12-Lead ECG f	X		X		X							X	X		X
Single, supine BP and pulse rate, and temperature f	X		X		X							X	X		X
FSH g	X														
Pregnancy test (WOCBP only)	X	X										X			X
HIV, HBsAg, HBcAb, HCVAb, syphilis	X														
COVID-19 testing	X h					X									

PFIZER CONFIDENTIAL

Visit Identifier a Abbreviations used in this table may be found in Appendix 8 .	Screening		Treatment Phase											Follow-Up b	Early Termination/ Discontinuation	
			-28 to -2	-1	1	2	3	4	5	6	7	8	9	10	11	
Urine drug test	X	X														
Study intervention administration (QD) i			X	X	X	X	X	X	X	X	X	X	X	X		
Skin Irritation Evaluation j			X	X	X	X	X	X	X	X	X	X	X	X	X	
CCI																
CRU discharge l															X	
Serious and nonserious AE monitoring m	X	→	→	→	→	→	→	→	→	→	→	→	→	→	X	X
PK blood sampling n			X	X		X			X			X	X			X

- Day relative to start of study intervention (Day 1).
- All cohorts: Follow-up contact to occur 28-31 days post last dose with a phone call; additional follow-up at investigator discretion, including to monitor open AE, or based on emerging data.
- Participants will be admitted at least 12 hours prior to dosing. Admission procedures will be conducted once, unless deemed necessary by investigator or sponsor.
- Physical examination may be performed at non-specified timings if there are findings during the previous exam or new/open AEs, if appropriate and at investigator discretion.

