- For screening visit, test results must be reviewed and deemed acceptable in order to proceed with participation in study.
- 12-lead ECGs, BP, pulse rate and temperature will be collected at screening. For Days 1, 4, and 10, ECGs, BP, pulse rate, and temperature will be collected prior to and at approximately 6 hours post-dose. Day 11 is 24 hours post-dose on Day 10 and is prior to discharge.
- For confirmation of postmenopausal status only.
- COVID-19 viral test to occur between Day -5 and Day -3 to permit availability of test result prior to admission on Day -1.
- Study intervention (PF-07038124 or vehicle) will be applied QD in the AM. Refer to [Section 6.1.1](#) for additional details.
- Skin irritation assessment of the application sites will be conducted on Days 1-10 prior to each application of the study intervention and 24 hours post-dose on Day 10. Refer to [Section 8.2.5](#).
- CRU discharge should occur following collection of PK sample at 24 hours post-dose on Day 10. Participants who have AEs or dermatological

Visit Identifier a Abbreviations used in this table may be found in Appendix 8 .	Screening	Treatment Phase											Follow-Up b	Early Termination/ Discontinuation	
		-1	1	2	3	4	5	6	7	8	9	10	11		
Days Relative to Day 1	-28 to -2	-1	1	2	3	4	5	6	7	8	9	10	11	38+3	

observations on Day 11 will return to the CRU up to the discretion of the investigator, and follow-up contact will be made.

- m. If unexpected reactions (eg, rash, hives) other than irritation reactions outlined in [Table 4, Section 8.2.5](#) occur at an application site, the application site location must be recorded.
- n. Refer to Pharmacokinetic Sampling Schedule table below.

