**Diagnostic Assessments:**

10. A positive urine drug test at screening and/or Day -1.
11. Screening supine BP  $\geq 140$  mm Hg (systolic) or  $\geq 90$  mm Hg (diastolic), following at least 5 minutes of supine rest. If BP is  $\geq 140$  mm Hg (systolic) or  $\geq 90$  mm Hg (diastolic), the BP should be repeated 2 more times and the average of the 3 BP values should be used to determine the participant's eligibility.
12. Baseline 12-lead ECG that demonstrates clinically relevant abnormalities that may affect participant safety or interpretation of study results (eg, baseline QTcF interval

>450 msec, complete LBBB, signs of an acute or indeterminate-age myocardial infarction, ST-T interval changes suggestive of myocardial ischemia, second- or third-degree AV block, or serious bradyarrhythmias or tachyarrhythmias). If the baseline uncorrected QT interval is >450 msec, this interval should be rate-corrected using the Fridericia method and the resulting QTcF should be used for decision making and reporting. If QTcF exceeds 450 msec, or QRS exceeds 120 msec, the ECG should be repeated 2 more times and the average of the 3 QTcF or QRS values should be used to determine the participant's eligibility. Computer-interpreted ECGs should be overread by a physician experienced in reading ECGs before excluding participants.

13. Participants with ANY of the following abnormalities in clinical laboratory tests at screening, as assessed by the study-specific laboratory and confirmed by a single repeat test, if deemed necessary:

- AST or ALT level  $\geq 1.5 \times$  ULN;
- Total bilirubin level  $\geq 1.5 \times$  ULN; participants with a history of Gilbert's syndrome may have direct bilirubin measured and would be eligible for this study provided the direct bilirubin level is  $\leq$  ULN.

14. A positive COVID-19 test at screening.

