### **8.2.3. Electrocardiograms**

Standard 12-lead ECGs utilizing limb leads (with a 10 second rhythm strip) should be collected at times specified in the [SoA](#) section of this protocol using an ECG machine that automatically calculates the heart rate and measures PR, QT, and QTcF intervals and QRS complex. Alternative lead placement methodology using torso leads (eg, Mason-Likar) is not recommended given the potential risk of discrepancies with ECGs acquired using standard

limb lead placement. All scheduled ECGs should be performed after the participant has rested quietly for at least 10 minutes in a supine position.

To ensure safety of the participants, a qualified individual at the investigator site will make comparisons to baseline measurements. Additional ECG monitoring will occur if a) a postdose QTcF interval is increased by  $\geq 60$  msec from the baseline **and** is  $>450$  msec; or b) an absolute QTcF value is  $\geq 500$  msec for any scheduled ECG. If either of these conditions occurs, then 2 additional ECGs will be collected approximately 2 to 4 minutes apart to confirm the original measurement. If the QTcF values from these repeated ECGs remain above the threshold value, then a single ECG must be repeated at least hourly until QTcF values from 2 successive ECGs fall below the threshold value that triggered the repeat measurement.

If a) a postdose QTcF interval remains  $\geq 60$  msec from the baseline **and** is  $>450$  msec; or b) an absolute QTcF value is  $\geq 500$  msec for any scheduled ECG for greater than 4 hours (or sooner, at the discretion of the investigator); or c) QTcF intervals get progressively longer, the participant should undergo continuous ECG monitoring. A cardiologist should be consulted if QTcF intervals do not return to less than the criterion listed above after 8 hours of monitoring (or sooner, at the discretion of the investigator).

In some cases, it may be appropriate to repeat abnormal ECGs to rule out improper lead placement as contributing to the ECG abnormality. It is important that leads be placed in the same positions each time in order to achieve precise ECG recordings. If a machine-read QTcF value is prolonged, as defined above, repeat measurements may not be necessary if a qualified medical provider's interpretation determines that the QTcF values are in the acceptable range.

ECG values of potential clinical concern are listed in [Appendix 7](#).

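### The mandatory QTc withdrawal rule needs a triplicate average, but for baseline QTcF below 390 msec a rise above 60 msec can occur without any repeat ECG being required

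*Protocol*

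**What the plan says.** Protocol Section 7.1, under ECG Changes, states: "A participant who meets either bulleted criterion based on the average of triplicate ECG readings will be withdrawn from the study intervention". The two criteria are a QTcF above 500 msec and "Change from baseline: QTc >60 msec". The second has no absolute floor.

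The Schedule of Activities lists the scheduled recording as "Single, supine 12-Lead ECG", and its timing footnote adds: "For Days 1, 4, and 10, ECGs, BP, pulse rate, and temperature will be collected prior to and at approximately 6 hours post-dose". One more recording follows on Day 11.

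Repeat recordings are governed by Section 8.2.3. It begins "Additional ECG monitoring will occur if a) a postdose QTcF interval is increased by" 60 msec or more and, in the same limb, also exceeds 450 msec. The alternative limb is an absolute value of 500 msec or more. Then: "If either of these conditions occurs, then 2 additional ECGs will be collected approximately 2 to 4 minutes apart to confirm the original measurement". Elsewhere in that section repeats are left to judgement: "In some cases, it may be appropriate to repeat abnormal ECGs to rule out improper lead placement as contributing to the ECG abnormality".

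Exclusion criterion 12 in Section 5.2 gives only an upper QTcF limit, 450 msec. Nothing excludes a low baseline.

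**The concern.** A stopping rule works only if the protocol requires the data it is applied to. Here the rule is judged on three readings, the schedule supplies one, and the clause that supplies the other two is narrower than the rule it serves. The change criterion in Section 7.1 stands alone, whereas the matching repeat trigger in Section 8.2.3 also demands a value above 450 msec. Between the two lies a zone in which a single reading has passed the withdrawal threshold and a site following Section 8.2.3 to the letter need not repeat it.

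The risk is to participants. Someone whose triplicate average would exceed +60 msec could go on being dosed because that average was never taken. Section 7.1 also has the site inform the sponsor's medical monitor or clinician once the discontinuation criteria are triggered. Without the triplicate, that notice may not be triggered either.

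**Working it through.** The plan states no figure to reproduce here, so the check compares the two rules directly.

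**Inputs.** Let B be baseline QTcF and P a single postdose QTcF, both in msec.

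- Withdrawal level (Protocol 7.1): P > 500, or P − B > 60. The change bullet says QTc; I read it as QTcF, the only correction the protocol uses.
- Mandatory repeats (Protocol 8.2.3): (P − B ≥ 60 and P > 450), or P ≥ 500.
- Eligible baselines (Protocol 5.2, criterion 12): upper limit 450, no lower limit.

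**Absolute criterion.** Any P > 500 also satisfies P ≥ 500, so repeats are always triggered. There is no gap.

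**Change criterion.** A reading falls in the gap when P − B > 60 and P ≤ 450. Both can hold only if B + 60 < 450, that is, B < 390. In whole msec the uncovered readings run from B + 61 to 450, which is 390 − B values:

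| Baseline | Uncovered readings | Count (390 − B) |
|---|---|---|
| 350 | 411–450 | 40 |
| 360 | 421–450 | 30 |
| 370 | 431–450 | 20 |
| 380 | 441–450 | 10 |
| 389 | 450 | 1 |
| 390 or more | none | 0 |

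For example, B = 370 and P = 435 gives a rise of 65, above the withdrawal threshold. But 435 does not exceed 450 and is below 500, so neither repeat trigger fires.

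Enumerating every whole-msec pair with B from 330 to 450 and P from B to 560 finds 1,830 pairs in the gap. This equals the sum 1 + 2 + … + 60 for baselines 389 down to 330. All have B ≤ 389 and P ≤ 450. These counts show the extent of the zone, not how likely it is to be entered.

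**Dosing at stake.** There are 10 daily doses. On the footnote's days, each participant has 6 scheduled ECGs after the first dose:

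| ECG | Doses still to come |
|---|---|
| Day 1, 6 h | 10 − 1 = 9 |
| Day 4, predose | 10 − 3 = 7 |
| Day 4, 6 h | 10 − 4 = 6 |
| Day 10, predose | 10 − 9 = 1 |
| Day 10, 6 h | 0 |
| Day 11 | 0 |

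Withdrawal can change dosing at four of the six. After the Day 4 six-hour ECG, the doses of Days 5 to 9 (five) are given before the next scheduled ECG.

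These counts follow the footnote. In the extracted Schedule of Activities grid the corresponding mark appears under Day 3, which may be an artefact of text extraction. On that reading the doses left would be 8 and 7 instead of 7 and 6, with six doses before the next ECG. The gap itself is unaffected.

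**After the fix.** With repeats required when P − B ≥ 60 or P ≥ 500, the same enumeration leaves 0 uncovered pairs.

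**The case against.** The strongest reply is that Section 7.1 never says its triplicate comes from Section 8.2.3. A site seeing +65 msec on one ECG can apply a mandatory rule only by taking three, so Section 7.1 may imply the repeats and what is missing is a cross-reference. It is true that the link is an inference. But Section 7.1 gives no trigger for taking the readings, scheduled ECGs are single, and no other text requires postdose repeats. The sections can be reconciled by a sensible reader, but they do not oblige one to do so.

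Second, such a rise is unlikely to go unnoticed. Section 8.2.3 requires comparison with baseline; Section 7.1 requires documented investigator review and a decision on clinically significant findings; Section 8 asks for prompt discussion of safety issues with the sponsor; Section 9.4.6 has ECGs reviewed during the study; and Appendix 7 lists a rise of at least 60 msec, with no floor, among its alerts. These do reduce the risk. None calls for a triplicate, and they put judgement where Section 7.1 intends a fixed rule.

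Third, the 450 msec floor may be deliberate, since lower values lie within the eligibility limit. That would make sense for escalating monitoring. As a condition for confirming the withdrawal criterion it conflicts with Section 7.1, which has no floor, and with the QTcF tables in Protocol 9.4.2.1 and SAP 6.1.4, which class an increase above 60 msec as severe separately from the absolute value.

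Fourth, Section 8.2.3 lets a qualified reader's interpretation remove the need for repeats, so even outside the zone they are conditional. That is correct, but the provision replaces a machine value judged acceptable; it does not excuse a confirmed prolongation.

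Finally, the event should be rare: eight participants receive active drug, it is topical, predicted exposure is about 3- to 6-fold below the minipig NOAEL exposure, and the earlier study in healthy participants reported no clinically meaningful ECG findings. This stands, and it limits the weight of the point.

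**Conclusion.** The concern holds. For any baseline QTcF below 390 msec there is a range of postdose values, from just above baseline + 60 up to 450 msec, that passes the Section 7.1 change threshold without the protocol requiring the readings needed to apply it. The 390 and 450 msec bounds are exact. The gap is confined to this zone.

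The conclusion assumes that the triplicate means the original ECG plus the two repeats, and that QTc in the change bullet means QTcF. How many participants will have a baseline below 390 msec cannot be known from the documents, so no probability is attached. The likely number of affected participants is small. The point merits a change because the rule protects participants and closing the gap costs almost nothing.

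**What to change.** Add one sentence to Section 8.2.3 or 7.1: any single postdose ECG with a QTcF increase from baseline of 60 msec or more, whatever its absolute value, leads to two additional ECGs, and withdrawal is judged on the average of the three. Keep the trigger at an absolute value of 500 msec or more. Keep the above-450-msec condition for escalation to hourly and continuous monitoring, so that burden does not widen. The provision for a qualified reader to overrule a machine value can stay.

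While editing, write QTcF in the second bullet of Section 7.1. This does not close the gap, but it makes both criteria use the same correction.

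The cost is a short wording change and two extra ECGs for each reading in the zone.
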